5) Activities of daily living (ADL): the cognitive function of the subjects was assessed in the baseline period, 2 weekends, 4 weekends, 8 weekends, 12 weekends, 26 weekends, 38 weekends and 52 weekends.

Safety evaluation

1) Vital signs: the temperature, pulse and blood pressure of the subjects were monitored at the end of the baseline period, 2 weekends, 4 weekends, 8 weekends, 12 weekends, 26 weekends, 38 weekends and 52 weekends.

2) Adverse event report: adverse event records were made on the subjects at the end of the baseline period, the end of the 2nd week, the end of the 4th week, the end of the 8th week, the end of the 12th week, the end of the 26th week, the end of the 38th week and the end of the 52nd week.

3) Treatment Emergent Symptom Scale (TESS): during the baseline period, the subjects were evaluated for side effects at the end of 2 weeks, 4 weeks, 8 weeks, 12 weeks, 26 weeks, 38 weeks, and 52 weeks.

4) Laboratory examination and electrocardiogram: routine blood test, biochemical examination and electrocardiogram examination were conducted at the end of the

screening period, the end of the 4th week, the end of the 12th week, the end of the 38th week and the end of the 52nd week.

Efficacy index

1) Main efficacy indicators:

At the end of the 12th week after treatment, the change value of ADAS cog scale scores of the subjects in the two groups compared with the baseline.

2) Secondary efficacy indicators:

1. At each follow-up point, the change value of ADAS cog scale scores of the two groups compared with the baseline.

2. At each follow-up point, the change value of hrsd-17 score of the subjects in the two groups compared with the baseline;

3. At each follow-up point, the change value of HAMA scale scores of the two groups compared with the baseline.

4. At each follow-up point, the change value of GDS score of the subjects in the two groups compared with the baseline.

5. At each follow-up point, the change value of NPI scale scores of the subjects in the two groups compared with the baseline.

6. At each follow-up point, the change value of ADL scale scores of the subjects in the two groups compared with the baseline.

7. Complete remission rate: the difference in the proportion of patients with a total score of hrds-17 ≤ 7 at each visit point between the two groups.

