8. Effective rate of treatment: the proportion difference between the two groups of subjects in the reduction rate of hrds-17 scale at each visit point and the baseline $\geq 50\%$.

9. Recurrence rate and recurrence time: recurrence is defined as any of the following conditions: the subject meets the DSM-IV diagnostic criteria for depressive episode; The subject was hospitalized again due to depression; After the treatment was effective (ham-d17 score decreased by $\geq 50\%$ compared with the baseline), ham-d17 score increased by more than 30% compared with the baseline at any visit point; During the maintenance treatment period, after the treatment of the subjects is effective or remission, the proportion of relapse and the time of relapse between the two groups at each visit point;

Safety index:

i. Abnormal values of vital signs, laboratory examination and electrocardiogram examination during the study period.

II. Adverse events and adverse reaction reports during the study period.

Basis for determining sample size

According to the main research hypothesis of this study, the effect of comprehensive intervention group on improving patients' cognition is better than that of conventional treatment group. According to the previous similar research results and the expected efficacy hypothesis, the difference between the groups of the study group and the control group in terms of ADAS cog score reduction after 12 weeks of treatment is about 2.2, and the combined standard deviation is 4. Set $\alpha = 0.025$ (one side), $\beta = 0.20$, and set the superiority and effectiveness limit value as 3 in combination with the

previous research and clinical significance, The ratio of the number of cases in the study group to the control group was 1:1. The sample size of the study group was 51 cases, and the sample size of the control group was 51 cases. Considering the 20% rejection rate of similar items, 64 cases need to be included in the study group and the control group.

Statistical analysis methods

Full Analysis Set (FAS): A collection of all randomized cases with valid baseline assessments. FAS is the main analysis set. Secondary efficacy measures were analyzed using only FAS without carry-over.

General principles: Statistical analysis was performed using SAS.9.4 statistical analysis software. P value < 0.05 was statistically significant (unless otherwise specified).

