Statistical description: Measurement data are described using mean (standard deviation), median (interquartile range), minimum value, and maximum value; skewed distribution indicators are normally corrected before analysis, unless otherwise specified. Enumeration data were described using the number of cases (percentage).

Statistical analysis methods

Full Analysis Set (FAS): A collection of all randomized cases with valid baseline assessments. FAS is the main analysis set. Secondary efficacy measures were analyzed using only FAS without carry-over.

General principles: Statistical analysis was performed using SAS.9.4 statistical analysis software. A P value < 0.05 was statistically significant (unless otherwise specified).

Statistical description: Measurement data are described using mean (standard deviation), median (interquartile range), minimum value, and maximum value; skewed distribution indicators are normally corrected before analysis, unless otherwise specified. Enumeration data were described using the number of cases (percentage).

1) Efficacy analysis:

Primary Endpoint Analysis

The between-group difference in the change from baseline in the total score of the two groups of subjects (ADAS-cog) at the end of 12 weeks

Statistical analysis of changes from baseline in ADAS-cog total scores at the end of 12 weeks was performed using MMRM (mixed model for repeated measures). The model takes the change of ADAS-cog total score at each time point after treatment relative to the baseline as the dependent variable, the baseline ADAS-cog total score is a covariate, and the grouping is a fixed effect. Each fixed effect factor and covariate is nested in each visit. Inside. According to the model, the adjusted mean of the total ADAS-cog total score at the end of treatment in each group compared with the baseline, as well as the difference of the adjusted mean between the two groups and its 95% confidence interval, the lower limit of the confidence interval and the set optimal value were calculated. The comparison of the effect-media value was used as the criterion for superiority.

Secondary endpoint analysis:

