Efficacy evaluation indicators include HRSD-17, HAMA, GDS, NPI, ADL and other scales. The differences between groups at the visit point relative to the baseline value were analyzed using the same analysis method as the main efficacy indicators. The cumulative complete remission rate, treatment response rate, recurrence rate and other outcome indicators during the study period were compared between groups using the Kaplan-Meier curve, and the COX proportional hazards model was used to evaluate the impact of the intervention while controlling for confounding factors such as disease duration.

Safety analysis: The incidence of adverse events and adverse reactions was tested by chi-square and described in a list.

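### Remission (clearly) and response (on the more natural reading) are defined as differences in proportions at each visit, but the only planned comparison is cumulative, by Kaplan-Meier and Cox

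*Combined protocol and SAP*

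**What the plan says.** All references are to the combined protocol and SAP.

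- **Secondary efficacy indicators, item 7 (complete remission):** "the difference in the proportion of patients with a total score of hrds-17 ≤ 7 at each visit point between the two groups".
- **Item 8 (effective rate):** "the proportion difference between the two groups of subjects in the reduction rate of hrds-17 scale at each visit point". The sentence then goes on to the baseline and the 50% threshold.
- **Item 9 (recurrence):** this names both a proportion and a time, "the proportion of relapse and the time of relapse between the two groups at each visit point".
- **Secondary endpoint analysis, rating-scale outcomes (HRSD-17 among them):** "The differences between groups at the visit point relative to the baseline value were analyzed using the same analysis method". The method meant is that of the primary endpoint, the MMRM on change from baseline.
- **Secondary endpoint analysis, event outcomes:** "The cumulative complete remission rate, treatment response rate, recurrence rate and other outcome indicators during the study period" are compared by Kaplan-Meier curve, with a Cox model adjusting for factors such as disease duration.
- **Full Analysis Set:** "Secondary efficacy measures were analyzed using only FAS without carry-over".
- **Symptomatic assessment:** HRSD-17 is rated at baseline and at weeks 2, 4, 8, 12, 26, 38 and 52.

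**The concern.** The proportion in remission at a visit is a matter of current status. A Kaplan-Meier curve for first remission shows how many have ever reached it by then. Both states can be lost over 52 weeks, and item 9 shows that the authors expect some patients to relapse after responding. Once benefit is lost, the two quantities separate.

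Followed as written, the plan would report who reached remission or response and how soon. It would not report the difference in the proportion remitted at a visit, which is what item 7 asks for. With definition and method at odds, the choice between a by-visit and a cumulative result could also be made after the data are seen.

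**Working it through.** **1. Does any other part of the plan supply the by-visit contrast?**

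- The by-visit MMRM is for change in scale scores. A mean difference in HRSD-17 change is not a difference in the proportion at or below 7.
- Under Statistical description, categorical data get counts and percentages. The by-visit percentages could therefore be tabulated, but with no planned between-group estimate, interval or test.
- Chi-square is named only under Safety analysis: "The incidence of adverse events and adverse reactions was tested by chi-square and described in a list".
- If the word cumulative qualifies only remission, response is still assigned to Kaplan-Meier/Cox.

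So the contrast in item 7, and in item 8 on the by-visit reading, has no planned analysis.

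**2. How far apart can the two quantities be?**

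The documents give no rates, so every rate below is assumed. Let c be the cumulative proportion attaining remission in an arm, and l the share of those who are out of remission at the later visit, with no new remissions in between. Then

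by-visit difference = c1(1 − l1) − c0(1 − l0).

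| Cumulative | Loss | Status at visit | Cumulative difference | By-visit difference |
|---|---|---|---|---|
| 40% v 20% | 0% v 0% | 40% v 20% | 20 | 20 |
| 40% v 20% | 10% v 10% | 36% v 18% | 20 | 18 |
| 40% v 20% | 30% v 30% | 28% v 14% | 20 | 14 |
| 40% v 20% | 50% v 50% | 20% v 10% | 20 | 10 |
| 40% v 40% | 30% v 30% | 28% v 28% | 0 | 0 |
| 40% v 40% | 30% v 40% | 28% v 24% | 0 | 4 |
| 40% v 40% | 30% v 50% | 28% v 20% | 0 | 8 |
| 40% v 40% | 50% v 30% | 20% v 28% | 0 | −8 |

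The differences diverge when loss differs between arms, or when loss is equal but cumulative rates differ. They agree when nothing is lost.

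A model that allows re-entry behaves the same way. Take seven visits and a 25% chance per visit of entering remission in both arms. Cumulative first remission is 1 − 0.75^7 = 86.7% in each arm. With a per-visit chance of loss of 10% v 20%, week-52 status is 67.9% v 54.7% (13 points). With 10% v 30% it is 67.9% v 45.3% (23 points). With equal loss both differences are zero.

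**3. How precise would a by-visit difference be?**

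The plan gives no precision or power figure for remission or response. The arm sizes come from Basis for determining sample size, which concerns the primary endpoint: 51 per arm, and 64 after a 20% allowance. Leaving aside the superiority limit stated there, which is a separate matter, 2 × [4 × (1.96 + 0.8416)/2.2]² = 51.9, close to the stated 51; and 51/0.8 = 63.75, rounded up to 64.

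SE = √[p1(1 − p1)/n + p0(1 − p0)/n]; half-width = 1.96 × SE; power by normal approximation, two-sided 0.05, unpooled SE.

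| Assumed status | n per arm | SE | 95% half-width | Power |
|---|---|---|---|---|
| 28% v 20% | 51 | 0.0842 | 16.5 points | 16% |
| 28% v 20% | 64 | 0.0752 | 14.7 points | 19% |
| 28% v 14% | 51 | 0.0795 | 15.6 points | 42% |
| 28% v 14% | 64 | 0.0709 | 13.9 points | 51% |

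The 51 per arm is planned for week 12, and no later retention is stated, so intervals at weeks 26 to 52 may be wider.

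**4. Number of contrasts.** 2 endpoints × 7 post-baseline visits = 14.

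**The case against.** **The phrase may mean only assessed at each visit.** In item 8 the words about the visit point run on to the baseline, so they may describe only the score reduction from baseline to visit. The English is awkward throughout, and word order is weak evidence. This stands for item 8: the by-visit reading is the more natural one, not the only one. It has less force for item 7, which attaches the visit to a difference in proportions.

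**Item 9 uses the same phrase and is left to Kaplan-Meier/Cox.** This suggests the authors saw the phrase as compatible with a survival curve. But item 9 also names time, and first relapse is a natural event endpoint. Items 7 and 8 name only proportions.

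**Loss of benefit is already partly analysed.** This is true. Item 9 counts a return of symptoms after response, and HRSD-17 change is compared by MMRM. Differential loss would not go wholly unseen, but neither analysis gives the defined proportions. For example, with a baseline of 18, a patient who moves from 7 to 8 leaves remission but is still a responder (8 ≤ 9), and the 1-point rise is below 30% of baseline (5.4 points).

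**The sizes are hypothetical.** This also stands. They show that the two comparisons can differ, not that they will in this trial.

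**Stronger readings a reader might infer.** One is that the plan contradicts itself outright on both endpoints; item 8's wording is too loose for that. Another is that the remission results will be materially misleading; with no rates in the documents, that cannot be shown. A third is that the silence on event rule (first or sustained), time origin and censoring makes the mismatch worse. That silence is a separate specification gap and would remain even if definition and method agreed.

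**Conclusion.** The point holds as a conflict between definition and method: clearly for item 7, and on the more natural reading for item 8. If the event is first attainment, the planned Kaplan-Meier/Cox comparison does not estimate the defined by-visit difference once remission or response can be lost. The size is unknown, and the differences shown rest entirely on assumed rates.

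The impact is minor and confined to secondary endpoints. The primary ADAS-cog analysis and the sample size are not affected.

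**What to change.** Make the Secondary endpoint analysis and items 7 and 8 agree. Two options are equally acceptable, depending on what was meant.

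**Option A: status at a visit.**
- In the FAS, without carry-over, report the between-group risk difference with 95% CI in remission and in response status at each visit.
- Use a repeated-measures binary model with group, visit, group-by-visit and baseline HRSD-17. Obtain the risk difference from an identity link, or by marginal standardisation from a logit link. Where events are too sparse for the model, give the unadjusted difference with its CI.
- State how missing HRSD-17 values are handled, for example by multiple imputation under missing at random.
- Name one key visit (week 12 would match the primary endpoint). Label the other visits descriptive, outside the general P < 0.05 rule.
- Keep Kaplan-Meier/Cox for recurrence and as a supportive time-to-first-event analysis.

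**Option B: time to attainment.** Reword items 7 and 8 as time to first (or sustained) remission and response, and keep Kaplan-Meier/Cox.

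Wherever Kaplan-Meier/Cox is kept for remission or response, state the event, time origin and censoring rule.

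**Cost.** Option A needs wording and one model (plus imputation if used) on HRSD-17 data already scheduled at every visit. Its drawback is imprecision: a half-width of about 15 to 17 points at an assumed 28% v 20%, possibly wider after week 12. It serves estimation rather than reliable detection of gaps of that size, and may be less precise than a time-to-first-event comparison. Option B needs only wording but gives up the by-visit comparison.
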